4.5.1 Visit Windows

Subject visit dates must be scheduled within the visit windows detailed in the Schedule of Study Visits table. One week equals 7 days (± 3 days). During the Screening Phase, each visit is scheduled, with reference to the allowed visit window. During the Treatment Phase, each visit is also scheduled with reference to the allowed visit window.

Confidential Page 22 of 73

TABLE 1: SCHEDULE OF VISITS. LIGHT GREY (SCREENING); LIGHT YELLOW (TREATMENT); LIGHT BLUE (END OF TREATMENT VISIT); LIGHT PURPLE (ADDITIONAL WOUND HEALING CONFIRMATION VISIT FOR THOSE WOUNDS THAT HEAL)

			Wk 1 TV1		Wk 2	Wk 3	Wk 4	Wk 5	Wk 6	Wk 7	Wk 8	Wk 9	W 10	W 11	W 12	W 13*	
Visit	SV1	SV2	Pre Rand	Post Rand	TV2	TV3	TV4	TV5	TV6	TV7	TV8	TV9	TV10	TV11	TV12	EOS 1	HCV1
Weeks from Randomization Date	-2	-1	0		1	2	3	4	5	6	7	8	9	10	11	13	2 weeks after initial healing
Window Period	±3 days	±3 days	±3 da	ays**	±3 days	±3 days	±3days										
Assessment of eligibility	х	х	х														
Informed consent	Х																
Ulcer history	Х																
Demographics	Х																
Medical History or changes	х	Х	х		Х	Х	х	Х	Х	Х	х	Х	Х	х	Х	Х	х
Prohibited Therapies assessment	х	х	х		х	х	х	х	х	х	х	х	х	х	х	х	х
Medication assessment	х	х	х		х	х	х	х	х	х	х	х	х	х	х	х	х
ABI/SPP/TCOM/ TBI or arterial Doppler study	x																
Randomization				Х													
WOUND-Q instrument assessment	x					x				x						х	
Ulcer assessments	Х	Х	Х		Х	Х	Х	Х	Х	Х	Х	Х	Х	X	Х	Х	
Infection assessment of index ulcer	х	х	х		x	X	х	Х	X	Х	x	Х	х	X	Х	Х	
Physical exam or changes	х	х	х		х	Х	х	х	Х	х	х	Х	х	х	Х	Х	х
Vital signs	Х	Х	Х		Х	Х	Х	Х	Х	Х	Х	Х	Х	Х	Х	Х	Х
Assess for Adverse Effects and Adverse Events					x	x	x	x	x	x	x	х	x	x	х	х	Χ ^[A]

Confidential Page 23 of 73

			Wk 1	TV1	Wk 2	Wk 3	Wk 4	Wk 5	Wk 6	Wk 7	Wk 8	Wk 9	W 10	W 11	W 12	W 13*	
Visit	SV1	SV2	Pre Rand	Post Rand	TV2	TV3	TV4	TV5	TV6	TV7	TV8	TV9	TV10	TV11	TV12	EOS 1	HCV1
Urine or blood pregnancy test control (females of childbearing potential)	х								x								
Assurance of effective birth control (females of childbearing potential)	х								х								
Pain assessment	Х	Х	Х		Х	X	Х	Х	Х	Х	Х	Х	Х	Х	Х	X	Х
Monofilament Test with vibratory (10 point)	x	x	x		X	X	X	x	x	X	x	x	X	x	x	х	х
Serum Creatinine	Х																
Blood Sugar	Х	X	Х		Х	X	Х	Х	Х	Х	Х	Х	Х	Х	Х	Х	Х
HbA1c Lab	Х															Х	
Take X-ray to rule out osteomyelitis or bone infection	х																
SnapshotNIR	Х		Х		Х		Х			Х						Х	
Index ulcer photographs	х	х	Х		Х	Х	Х	Х	Х	Х	Х	Х	Х	Х	Х	х	х

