8.9 Pain Assessment: NPRS

Pain intensity of the reference DFU is to be assessed before any dressing changes or other ulcer manipulations at all screening and treatment visits.

The subject will be asked to indicate a numerical value that best represents the current pain intensity at the index ulcer site on a scale of 0 to 10, anchored by word descriptors at each end, as "no pain" on the left side and "worst possible pain" on the right side of the number line. The number 0 represents "no pain," the number 5 represents "moderate pain", and the number 10 represents the "worst possible pain." The subject indicates the level of pain intensity by selecting a number on the line shown in Figure 3 below that represents their perception of their current state.

[figure not shown]

FIGURE 3: SUBJECT PAIN SCALE (NPRS)

Confidential Page 45 of 73

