8.13 Semmes Weinstein Monofilament Test for Peripheral Neuropathy

This is a non-invasive topical evaluation of neuropathy with a monofilament wire and with vibratory evaluation. The test will be performed in a standard manner with 10 points being evaluated on each visit. At each point, the Investigator asks the subject whether they can feel the filament and / or vibration (yes or no). Note: If a subject is missing a body part called out in the Semmes Weinstein test and with vibratory, the most skin in the area where the missing body part is located is used for the test.

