Primary analysis: Proportion of index wounds closed at 12 weeks (group 1 versus group 2) using chi square. Analysis will be adjusted using logistic regression.

Secondary analysis: (1) proportion of Index Wounds closed at 6 weeks (group 1 versus group 2) using chi square; (2) time to heal within 6 and 12 weeks using Kaplan-Meier analysis; (3) PAR at 6 and 12 weeks (group 1 versus group 2) using the Mann-Whitney test; (4) mean difference between groups 1 and 2 of change in weekly peripheral neuropathy score surrounding the DFU using the Semmes Weinstein monofilament with vibratory procedure based on GLM repeated measures; (5) mean difference between groups 1 and 2 of change in WOUND-Q score based on difference between baseline and 12 weeks using t test if data are normal or Kolmogorov–Smirnov test if data are non-normal; and (6) mean difference between groups 1 and 2 of change in weekly wound pain VAS score based on GLM repeated measures.

Control of the familywise error rate (all endpoints) will be achieved through the Hochberg stepup procedure.

Every effort will be made to obtain required data at each scheduled evaluation from all subjects who have been randomized and treated. Subjects who are withdrawn or lost to follow-up will be included in the ITT analysis of primary and secondary endpoints using data imputation methods detailed in the SAP. Sensitivity analysis will also be conducted for the primary endpoint using different imputation algorithms.

10 Adverse Effects and Events (Definitions and Reporting)

The Investigator is responsible for the detection and documentation of any events meeting the criteria and definition of an adverse effect or adverse event (AE), as described in this protocol.

Confidential Page 50 of 73

During the study when there is a safety evaluation, the Investigator or site staff will be responsible for detecting, documenting, and reporting any adverse effect or adverse event, as detailed in this Section of the protocol.

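### Pain and neuropathy are planned as GLM repeated measures on weekly scores that end at healing or TV7 exit, with no rule for later scores; the WOUND-Q fallback test does not address the stated mean difference

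*Combined protocol and SAP*

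**What the plan says.** **Analysis.** Section 9.2 compares the arms on "change in weekly wound pain VAS score based on GLM repeated measures". Neuropathy change is also weekly, measured "using the Semmes Weinstein monofilament with vibratory procedure based on GLM repeated measures". WOUND-Q is a mean group difference in change from baseline to 12 weeks, "using t test if data are normal or Kolmogorov–Smirnov test if data are non-normal".

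**Measure and times.** Section 9.2 calls the pain score a VAS. The synopsis, section 3, section 8.9 and Table 4 call it the NPRS. The synopsis and section 3 list TV1, TV3, TV7, TV9 and EOS1 for pain and neuropathy. Section 8.9, however, says pain "is to be assessed before any dressing changes or other ulcer manipulations at all screening and treatment visits", section 8.13 says of the monofilament that "The test will be performed in a standard manner with 10 points being evaluated on each visit", and Table 1 marks both at every visit, including HCV1.

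**When scores stop.** Weekly visits run until healing or exit (4.3.1). EOS1 comes forward at healing, or when area reduction is under 50% at Week 7 (4.5, 4.5.3.3.3). A healed subject then has HCV1 two weeks later, and continues on the allocated schedule if the ulcer reopens before the end of the study (4.5.5).

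**Missing data.** The relevant sentence in 9.2 is: "Subjects who are withdrawn or lost to follow-up will be included in the ITT analysis of primary and secondary endpoints", with methods left to the SAP. Section 5.1 classes both healed subjects and TV7 exits as having completed the study.

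**Multiplicity.** "Control of the familywise error rate (all endpoints) will be achieved through the Hochberg stepup procedure" (9.2).

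**The concern.** Classical GLM repeated measures drops any subject who lacks one of the modelled values. Here the values that run out are those of subjects who healed early and of subjects who exited at TV7. Neither group is withdrawn or lost, so the imputation sentence reaches neither. The comparison would then be made mainly among subjects with a slow or unhealed ulcer who passed TV7. That is not the randomized comparison, and it can hide a benefit in pain or sensation that comes with healing.

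For WOUND-Q, the named quantity is a difference in means, but the fallback responds to any difference between the distributions. A significant result could reflect spread or shape alone. WOUND-Q is collected at SV1, TV3, TV7 and EOS1 (8.8). EOS1 can be early, and Table 1 steps from week 11 to week 13, so the visit that supplies the 12-week value also needs stating.

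**Working it through.** **1. The plan's own figure.** With 120 per arm, 0.70 v 0.35, pooled two-sided Z at 0.049 (all from 9.2):
- pooled SE = √(2 × 0.525 × 0.475 / 120) = 0.0645
- unpooled SE = √((0.21 + 0.2275) / 120) = 0.0604
- power = Φ((0.35 − 1.969 × 0.0645) / 0.0604) = 99.99%

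The stated 100% is reproduced. The protocol gives no power, SD or effect for pain, neuropathy or WOUND-Q.

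**2. Subjects without a complete series.** Healers: 120 × 0.70 = 84 and 120 × 0.35 = 42. Non-healers: 36 and 78.
- *Full weekly series.* Healing removes at most 84/120 = 70% v 42/120 = 35%. If 1 in 12 healers first close at the last visit (assumed), 7 v 3.5 are kept, and the loss is 64% v 32%.
- *Endpoint schedule (TV1, TV3, TV7, TV9, EOS1).* Only subjects closing before TV9 lose a value. TV2 to TV8 are 7 of the 12 post-baseline visits. If closures spread evenly (assumed), the loss is 0.70 × 7/12 = 41% v 0.35 × 7/12 = 20%. At 5/12 it is 29% v 15%, and at 9/12 it is 53% v 26%.

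TV7 exits add to this, and there are more non-healers in the FIBRACOL arm. The exit share is not given, so a range is shown. For the endpoint schedule at 7/12, the loss is (49 + 36 × share)/120 v (24.5 + 78 × share)/120. There is no other dropout.

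| TV7 exits among non-healers (assumed) | Weekly series, lost | Endpoint schedule, lost |
|---|---|---|
| 0% | 64% v 32% | 41% v 20% |
| 20% | 70% v 45% | 47% v 33% |
| 40% | 76% v 58% | 53% v 46% |
| 60% | 82% v 71% | 59% v 59% |

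(MIRRAGEN v FIBRACOL.) As exits rise, the total losses converge, but the arms lose different subjects: relatively more healers in one, more failures in the other.

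**3. Direction only.** Assume pain changes by −3 if healed and −1 if not, whatever the arm. All subjects: (0.70 × −3 + 0.30 × −1) − (0.35 × −3 + 0.65 × −1) = −2.4 + 1.7 = −0.7. Among non-healers only: −1 − (−1) = 0. The values are invented, so this shows a mechanism and not a size.

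**4. Kolmogorov-Smirnov with equal means.** Simulation with 120 per arm, 20,000 trials, nominal 5%. Shapes and SD ratios are assumed. The cells give rejection %, exact to asymptotic p-value.

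| Shape | SD ratio 1 | 1.25 | 1.5 |
|---|---|---|---|
| Normal | 3.4–4.8 | 8.9–12.2 | 29.5–37.9 |
| Gamma, shape 4 | 3.6–5.2 | 12.3–16.7 | 50.2–59.2 |
| Gamma, shape 2 | 3.5–5.1 | 18.9–24.7 | 77.5–83.7 |
| Laplace | 3.5–5.1 | 6.9–9.6 | 17.1–22.8 |

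Welch t stays at 4.7–5.2% in every cell. Under an assumed Shapiro-Wilk pre-test the fallback is used in 100% of gamma trials but only 9–10% of normal trials, so the non-normal rows matter more.

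**5. Effect on the primary.** Section 9.2 lists nine tests: closure at 12 and 6 weeks, time to heal at 6 and 12 weeks, PAR at 6 and 12 weeks, neuropathy, WOUND-Q and pain. At the strictest Hochberg step, 0.05/9, primary power is Φ((0.35 − 2.773 × 0.0645) / 0.0604) = 99.8%. At 0.05/20 it is still 99.5%.

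**The case against.** **The SAP is still to come.** Section 9.2 defers technical detail and imputation to a SAP due before database lock, and nowhere says that incomplete series are dropped. A reader might infer that the randomized comparison is already lost. The protocol does not support that: the problem is conditional on how the GLM is run. What remains is that the protocol names the method and limits its imputation sentence, and a model that keeps partial series still needs a rule for healed subjects.

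**70% v 35% is the worst schedule.** This stands. It applies only to a full weekly series. Unequal numbers alone also do not bias a mean difference; that requires the scores to depend on healing or exit.

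**Kolmogorov-Smirnov is a valid test.** A reader might infer an inflated type I error. That is not so: when the two distributions are equal it rejects in 3.4–5.2% of trials. The high figures are correct rejections of its own null hypothesis, and they show only that it answers a different question from the one stated. It can also be the stronger test. For a pure shift of 0.363 SD in gamma shape 2 data it has 87–90% power, against 80% for Welch t.

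**TV7 exits might be thought to fall under the imputation sentence,** because the Table 1 footnote mentions only healing or withdrawal as reasons for an early EOS1. Section 4.5 expressly gives TV7 exits an early EOS1, 5.1 calls them completers, and 5.2 lists them apart from withdrawn subjects. Their status is clear, and the sentence does not reach them.

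**Conclusion.** The point holds as a secondary-endpoint matter that the SAP should settle. The repeated-measures plan does not fit the follow-up design, no rule covers scores after healing or TV7 exit, and the WOUND-Q fallback does not match its stated quantity.

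The selection by outcome rests on complete-series analysis, an assumption about the method. Under it, healing removes up to 70% v 35% from a weekly series, or about 41% v 20% (29% v 15% to 53% v 26%) on the endpoint schedule, before TV7 exits. These use the plan's healing rates and an assumed spread of closures. The resulting error in the arm difference cannot be quantified from the protocol.

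The Kolmogorov-Smirnov mismatch is certain in kind. Its practical size depends on spread and shape, which the protocol does not give. A reader might infer from the all-endpoint Hochberg family that the primary result is at risk; at the planned rates its power stays at 99.8%, so that effect is negligible.

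**What to change.** 1. **Model.** Replace GLM repeated measures with a baseline-adjusted, likelihood-based mixed model (arm, visit, arm-by-visit) on every recorded score, and name a fallback covariance structure. Reconcile the weekly VAS wording in 9.2 with the NPRS and the visit list in the synopsis and section 3.
2. **After healing.** State one rule: the closure-visit score (or early EOS1 score) until HCV1, the HCV1 score afterwards, and observed values if the ulcer reopens and the subject continues. A subject first closed at TV6 (week 5) has HCV1 at week 7, so the TV6 score serves at TV7. Add a sensitivity analysis without carried scores, because carrying them forward understates uncertainty.
3. **After TV7 exit.** Treat scores as missing. Exit depends on ulcer area, so use the weekly area already recorded as an auxiliary variable, for example in multiple imputation. Carry the TV7 value forward as a sensitivity analysis.
4. **WOUND-Q.** Drop Kolmogorov-Smirnov and the normality pre-test. For each scale used (Appendix F lists five components), analyse change by ANCOVA on arm and baseline with robust or bootstrap intervals. In simulation with no arm effect and HC3 errors this rejected 4.4–5.4%. Keep Mann-Whitney as supportive only: it too rejects with equal means (11% and 22% for gamma shape 2 at SD ratios 1.25 and 1.5).
5. **Timing.** State which visit supplies the 12-week value and whether an early EOS1 counts. Confirm that the WOUND-Q baseline is SV1.

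**Cost.** SAP wording and some extra analysis. The closure visit and HCV1 already record pain and monofilament scores. Twelve-week results for healers will rest on the stated rule, and the TV7-exit assumption cannot be tested. Constant carried scores can strain an unstructured covariance over 12 visits (12 × 13 / 2 = 78 parameters). A mean-based test gives up power under a skewed pure shift (about 80% v 87–90% at 0.363 SD).

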published 40-patient pilot study in DFU which demonstrated a statistically significant 2.8 fold increase in healing rates compared to SOC alone (p=0,004) and doubled the rate of wound are reduction at all time points $(p-0.027)^{22}$.

Confidential Page 15 of 73

2 Rationale for Study

MIRRAGEN™ is a bioactive borate-based glass fiber matrix (BBGFM) that can dissolve in wound fluids over a period of several days. A recent 40-patient RCT and additional case studies involving the treatment of chronic diabetic foot ulcers (DFUs) with BBGFM suggest that when used as dressing as part of the standard of care (SOC), improved healing trajectories result. Based on this early promising data, a larger RCT is necessary to further validate these results. For consistency one type of wound will be studied in this trial and we have chosen DFU's as they are some of the most common wounds seen in the wound clinics.

Confidential Page 16 of 73

3 Study Endpoints

The purpose of this clinical evaluation is to collect patient outcome data on 2 commercially available standard of care dressings in partial/full-thickness diabetic foot ulcer subjects. Patient outcomes will be compared at 6 and 12 weeks.

The **primary endpoint** is the proportion of subjects that obtain complete closure over the 12-week treatment period.

Secondary endpoints include a comparison between groups of the following clinical measures:

- 1. The time to achieve complete wound closure of the target ulcer by the end of 12 weeks.
- 2. Percentage wound area reduction from TV1 to TV13 measured weekly with digital photographic planimetry and physical examination.
- 3. The number and type of Treatment Emergent Adverse Events.
- 4. Change in peripheral neuropathy of the target foot assessed using the standard 10-point Semmes-Weinstein monofilament exam [Time Frame: TV1, TV3, TV7, TV9, and EOS1].
- 5. Change in pain in the target ulcer assessed using the NPRS scale. [Time Frame: TV1, TV3, TV7, TV9, and EOS1].
- 6. Change in quality of life using WOUND-Q assessment.

Exploratory/Tertiary Endpoints

- 7. Difference in cellulitis and/or infection at 12 weeks.
- 8. Use of near-infrared tissue oxygenation imaging assessment of wounds at select sites to evaluate changes in vascularization/oxygenation of wounds with treatment (Kent Imaging SnapshotNIR; Time Frame: SV1, TV1 pre-randomization, TV2, TV4, TV7, and EOS1).

Confidential Page 17 of 73

4 Study Design

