9.2 Statistical Analysis

Descriptive statistical methods will be used to summarize the data from this study with hypothesis testing performed for the primary and other selected efficacy endpoints. All testing for endpoints will be two-sided with alpha set at .05 level of significance if no statistical testing is done at the interim analysis at 0.044 if statistical testing is done at N=240.

A formal Statistical Analysis Plan (SAP) will be created prior to database lock. The primary endpoint analysis will be at 12 weeks and a series of secondary and exploratory/tertiary

Confidential Page 49 of 73

endpoints will be analyzed at 6 and 12 weeks. The SAP will provide a more technical and detailed description of the proposed data analysis methods and procedures. Any deviation from the analyses outlined in the protocol will be described in the most current version of the SAP. All statistical analyses will be conducted using PASW 28.

The primary study hypothesis is that the proportion of wounds healed at 12 weeks, after up to 12 weeks of SOC with MIRRAGEN™ and SOC with FIBRACOL™, will be equal for Groups 1 and 2. Formally, H0: I1–I2 = 0; HA: I1–I2 = D1≠0, where I1 is the proportion of wounds healed in Group 1, I2 is same metric for Group 2, D1 is the difference (I1–I2); assuming the alternative hypothesis and statistical test used is chi square/Fisher exact test. Analysis may be adjusted using generalized linear modeling based on available variables at baseline known to affect wound healing.

Group sequential trials with sample sizes of 120 and 120 at the final look achieve 100% power to detect a difference of 0.35 between group 1 (the MIRRAGEN™ group) (proportion 0.70) the control group (SOC with FIBRACOL™) proportion of 0.35 at the 0.049 significance level (alpha) using a two-sided Z-Test (Pooled).

The populations defined for analysis will include the intent-to-treat (ITT) and per protocol (PP). Additional analysis populations may be defined to evaluate study results. Any additional analysis populations will be defined in the SAP.

Envelopes will be created with a random allocation sequence, which will be composed of a random sequence of block sizes of 10 designed to achieve a balanced design.

One interim analysis will be performed (N~100). The object of the interim analysis is to assess subject outcomes between the groups, in particular to assess any adverse effects or events, such as infection and to recalculate sample size for the primary endpoint.

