Appendix F: WOUND-Q Instrument

SCALE STRUCTURE

Protocols for interventions to treat and prevent wounds have typically overlooked the patient perspective of outcomes and have focused instead on objective measures. The WOUND-Q is a rigorously developed patient-reported outcome measure that can be used with all types of chronic wounds in any anatomical location. The WOUND-Q measures 4 overarching domains. Each domain includes 2 or more independently functioning scales. Clinicians and researchers are able to administer the subset of scales relevant to their situation.

WOUND CHARACTERISTICS

Three scales measure wound characteristics. The first scale measures how concerned someone is with their chronic wound(s) in the past week. The other two scales measure how bothered people are with drainage and smell.

HEALTH-RELATED QUALITY OF LIFE

Four scales measure health-related quality of life. The first scale measures life impact and the other three measure specific concerns, i.e., how chronic wound(s) affect sleep, psychological, and social function.

EXPERIENCE OF CARE

Four scales measure patients' experience of healthcare. The first scale measures satisfaction with information and the other three measure satisfaction with members of the health care team, i.e., home care nurses, wound team, and office staff in a wound clinic.

WOUND TREATMENT

Confidential Page 70 of 73

Two scales measure common treatments for chronic wounds. One scale measures satisfaction with dressing and the other scale measures satisfaction with the use of a suction device (e.g., vacuum pump device, negative pressure therapy dressing).

Data analysis

WOUND-Q Instrument

- 1. Wound Assessment
- 2. Wound Drainage
- 3. Wound Smell
- 4. Health-Related Quality of Life
- 5. Treatment Dressing

Confidential Page 71 of 73

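### Hochberg over all endpoints includes the primary, so a primary p of 0.02 is negative if pain, neuropathy and WOUND-Q all miss, although the primary was powered alone at 0.049

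*Combined protocol and SAP*

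**What the plan says.** All the decision rules are in protocol section 9.2.

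- **Primary test.** "Primary analysis: Proportion of index wounds closed at 12 weeks (group 1 versus group 2) using chi square"; a logistic regression adjustment is also planned.
- **Secondary tests.** Six numbered items: closure at 6 weeks, time to heal, percentage area reduction (PAR), neuropathy, WOUND-Q and pain. Some cover two time points, for example "time to heal within 6 and 12 weeks using Kaplan-Meier analysis".
- **Multiplicity.** Directly after that list: "Control of the familywise error rate (all endpoints) will be achieved through the Hochberg stepup procedure".
- **Power.** 120 per group, 0.70 v 0.35, stated power 100%, "at the 0.049 significance level (alpha) using a two-sided Z-Test (Pooled"). This is for 12-week closure only, with no allowance for other endpoints.
- **Alpha.** Endpoint tests are two-sided at 0.05 if nothing is tested at the interim, otherwise "at 0.044 if statistical testing is done at N=240". With 0.049 in the power statement, three values are in play.
- **Scope of testing.** The section opens with "hypothesis testing performed for the primary and other selected efficacy endpoints", which is narrower than all endpoints.

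Two other places bear on the size of the family. Section 3 counts "The number and type of Treatment Emergent Adverse Events" among the secondary endpoints. Appendix F says of WOUND-Q that "Each domain includes 2 or more independently functioning scales".

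**The concern.** Hochberg's procedure starts from the largest p-value in the family. If the primary is a member, the threshold it faces depends on how many other endpoints miss. Pain, neuropathy and WOUND-Q could plausibly show no difference even if the dressing closes more ulcers. A clear result on the powered endpoint could then be declared negative because of endpoints for which the trial was not sized.

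Two things are at stake. First, the test that was powered is not the test the plan will carry out. Second, the family is not listed, so two statisticians could apply the paragraph to the same data and reach different decisions on the primary. Type I error is not at stake: putting the primary in the family can only make its test stricter.

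**Working it through.** **Inputs, all from section 9.2:** 120 per group; 0.70 v 0.35; alpha 0.05, 0.049 or 0.044, two-sided; one primary and six numbered secondaries; Hochberg over all of them. The smaller effects in step 4 are assumptions and are not in the documents.

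**1. The plan's power figure.** Pooled two-proportion Z-test, with mean proportion p̄ = (p1 + p2)/2:

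- power = Φ[(|p1 − p2| − z·s0)/s1], where s0 = √(2p̄(1 − p̄)/n) and s1 = √(p1(1 − p1)/n + p2(1 − p2)/n)
- p̄ = 0.525, s0 = 0.0645, s1 = 0.0604, and z = 1.969 at two-sided 0.049
- (0.35 − 1.969 × 0.0645)/0.0604 = 3.69, so power is 99.99%

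The stated 100% is reproduced, for the primary tested alone.

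**2. The threshold under Hochberg.** Order the m p-values. Find the largest rank i with p(i) ≤ alpha/(m − i + 1), and reject ranks 1 to i. If three p-values exceed alpha, the three highest ranks fail at alpha, alpha/2 and alpha/3. Every remaining threshold is at most alpha/4:

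| Alpha | alpha/3 | alpha/4 |
|---|---|---|
| 0.05 | 0.0167 | 0.0125 |
| 0.049 | 0.0163 | 0.01225 |
| 0.044 | 0.0147 | 0.0110 |

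A primary p of 0.02 exceeds every alpha/4, and so does any p-value ranked above it. It cannot be rejected, whatever the family size and whatever the other endpoints show. Two missed secondaries are already enough, because 0.02 also exceeds every alpha/3.

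A direct run of the procedure used 7 and 9 tests, three secondaries at p = 0.30, 0.40 and 0.50, and all others at 0.001. A primary p of 0.02 or 0.013 was not rejected at any of the three alphas, 0.0125 was rejected only at 0.05, and 0.0110 was rejected at all three.

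**3. What this means in patients.** Control 42/120 (35%):

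| Healed on MIRRAGEN, of 120 | Chi-square p | Fisher p |
|---|---|---|
| 58 | 0.0362 | 0.0493 |
| 59 | 0.0262 | 0.0362 |
| 60 | 0.0188 | 0.0262 |
| 61 | 0.0132 | 0.0187 |
| 62 | 0.0092 | 0.0131 |

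Tested alone by chi-square, 58 to 61 healed is significant at all three alphas. If the three secondaries miss, it is negative at all three. With Fisher's exact test the affected range is 59 to 62.

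**4. Power when those three secondaries miss.** Same formula, alpha 0.049 against 0.01225 (z = 2.505):

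| Closure rates | Primary alone | At alpha/4 |
|---|---|---|
| 0.70 v 0.35 (design) | 99.99% | 99.91% |
| 0.60 v 0.35 (assumed) | 97.6% | 92.2% |
| 0.55 v 0.35 (assumed) | 87.9% | 73.3% |
| 0.50 v 0.35 (assumed) | 65.0% | 43.8% |

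The choice of alpha changes little. For 0.55 v 0.35 the fall is 88.1% to 73.5% starting from 0.05, and 86.9% to 72.0% starting from 0.044. Exact binomial enumeration at 0.049 and 0.01225 gives 87.2% and 72.8%. At the design effect, power is still 99.7% at 0.044/9.

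**5. Size of the family.** One primary plus six numbered items is 7 tests. Counting time to heal and PAR separately at 6 and 12 weeks makes 9. At alpha 0.05 the lowest possible threshold is 0.05/7 = 0.0071 or 0.05/9 = 0.0056, and lower if adverse events or several WOUND-Q scales are counted. The alpha/4 result does not depend on this count.

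**The case against.** The strongest reply is that the plan's own power claim survives: at 0.70 v 0.35, power at alpha/4 still rounds to the stated 100%. Large losses appear only when the true difference is 0.15 to 0.20, about half the design effect. They are also conditional on all three secondaries missing, and the documents give no expected effects from which to judge how likely that is. If every endpoint falls below alpha, Hochberg costs nothing. All of this stands, and the power losses should be read as a scenario.

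A second reply is that one Hochberg family including the primary is a recognised way to control familywise error. That is true. But it does not match a sample size paragraph that gives the primary its full alpha.

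A third is that the family is less vague than it looks. All endpoints can be read as those just listed, adverse events are neither efficacy endpoints nor on that list, and item 5 names a single WOUND-Q score. This has some force. What stays open is whether the 6- and 12-week tests count separately and how the five WOUND-Q instruments listed in Appendix F become one score. On this narrower reading the primary is still in the family.

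Finally, the sponsor may have meant the secondaries only, and section 9.2 defers detail to a SAP to be written before database lock. No text now says so. The trial is open label, with an interim look at outcomes by group, so settling the primary's threshold late would invite challenge.

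**Conclusion.** The concern holds and should be fixed. As written, section 9.2 places the primary in one Hochberg family with the secondaries, so a primary p of 0.02 is negative whenever pain, neuropathy and WOUND-Q each exceed alpha. This follows from the text and the procedure alone, for each of the three alphas and any family that contains these four tests.

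The size depends on the true effect. At the design effect the loss is under 0.1 percentage points. At an assumed difference of 0.20 it is 87.9 − 73.3 = 14.6 points, and at an assumed 0.15 it is 65.0 − 43.8 = 21.2 points. Both take 120 per arm and exactly the alpha/4 threshold; if further endpoints miss, the threshold can be lower still. The disagreement among 0.05, 0.049 and 0.044 is a separate matter and does not change the conclusion.

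**What to change.** In section 9.2 and the SAP, state that 12-week closure is tested first, alone, at the full final alpha, once 0.05, 0.049 and 0.044 have been reconciled to one value. Only if it is significant is Hochberg applied, at that same alpha, to a listed set of secondary tests. The list should say whether the 6- and 12-week tests count separately and which WOUND-Q score is tested. All other endpoints are reported descriptively.

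This keeps familywise control and makes the planned test the one that was powered. It takes one sentence in section 9.2 and a short list in the SAP, both before database lock. The price is that no confirmatory secondary claim can be made if the primary fails.
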